#### 4.6.2 Safety Endpoints

- Incidence (severity and causality) of any local skin reactions (LSRs) and systemic AEs.
- Number of subjects with presence (and severity) at each time point of the following LSRs: burning/stinging, erythema, erosions, and edema.
- Changes from Baseline in vital signs at Visit 6 (EOS).
- Changes from Baseline in clinical laboratory test results (chemistry, hematology, and urinalysis) at Visit 6 (EOS).
- AEs and SAE reported (severity, relatedness etc)

#### 4.6.3 Exploratory Endpoints

- Time to 2 or more points decrease from baseline in IGA
- Time to achieve a score of 0 for both IGA and VIIS scaling
- Time to achieve a score of 1 for both IGA and VIIS scaling
- Kapa agreement analysis for VIIS and IGA scores at each visit
- Correlation of IGA scores and VIIS scaling at each visit
- Correlation of IGA scores and VIIS target sites scores at each visit
- Proportion of subjects with VIIS treatment success by body region
- Proportion of subjects with VIIS treatment success by genetic mutation
- Proportion of subjects with IGA treatment success by genetic mutation
- Proportion of subjects with VIIS treatment success by phenotype
- Proportion of subjects with IGA treatment success by phenotype
- Proportion of subjects with VIIS treatment success by drug/BSA ratio
- Proportion of subjects with IGA treatment success by drug/BSA ratio
- Proportion of subjects with VIIS treatment success by drug/BMI ratio
- Proportion of subjects with IGA treatment success by drug/BMI ratio
- Proportion of subjects with VIIS treatment success by drug/kg ratio
- Proportion of subjects with IGA treatment success by drug/kg ratio
- Proportion of subjects with VIIS treatment success by Baseline BSA Stratification
- Proportion of subjects with IGA treatment success by Baseline BSA Stratification
- Proportion of subjects with VIIS treatment success by OTC steroid cream usage
- Proportion of subjects with IGA treatment success by OTC steroid cream usage
- Proportion of subjects with VIIS treatment success by assessment medium
- Proportion of subjects with IGA treatment success by assessment medium
- Proportion of subjects with VIIS treatment success by drug interruption
- Proportion of subjects with IGA treatment success by drug interruption
- Proportion of subjects who meet both the primary and major secondary endpoint
- Proportion of subjects who achieve VIIS- $\geq$ 75 at target body sites

- Proportion of subjects who achieve VIIS- $\geq$ 50 at non-target body sites
- Changes from Baseline in VIIS scaling, Active Vs Vehicle – MMRM analysis
- Changes from Baseline in I-NRS score, Active Vs Vehicle – MMRM analysis

## 5. DATA LISTINGS

### 5.1. Sources of Data

Data sets containing raw data will be provided by the Data Management group, extracted from the clinical study database of data entered into a Case Report Form (CRF). It is assumed that the database will contain the data from Screening through to the Follow-up Safety Visit of the study. Minimal information will be captured for screen failures.

Analysis datasets (SDTM and ADaM) will be generated from the data extracted from the study database, along with the following data entered separately or received from other sources:

- Randomization, from statistician responsible for its preparation
- Clinical laboratory safety data, provided by the clinical laboratory to Data Management at Avance Clinical

All data entered into the CRF or provided from other sources as described above will be presented (explicitly or implicitly) in data listings or figures as described in Appendix 1.

### 5.2. Randomization and Subject Identification Code

Subjects who meet all inclusion criteria and no exclusion criteria will be randomized to a treatment group in a 1:1:1 ratio, stratified by CI subtype.

All subjects will be centrally assigned to randomized study treatment using an Interactive Web Response System (IWRS). Before the study is initiated, the log in information and directions for the IWRS will be provided to each study center.

Study medication use will be accounted and dispensed at the study visits as summarized in the Schedule of Activities (Section 1.2 of the protocol).

Subjects will be assigned a randomization number formatted, Rsnn where s is an indicator for the CI subtype (1 = ARCI-LI, 2 = RXLI) and nn is the random permutation of 01 - 45.

The listings for inclusion in an appendix to the clinical study report will be prepared after the study has been unblinded.

In the listings, subjects will be identified by subject number (assigned at randomization), with treatment as a secondary grouping identifier. Screening number will be shown only on the listing of informed consent data and screen failure data.

### 5.3. Maintaining the Study Blind

In this double-blind study, all personnel involved, i.e., physicians, site staff, and subjects will remain blinded at all times, except in an emergency, where knowledge of the

randomization code is required to provide appropriate treatment. In case of an emergency, the Investigator has the sole responsibility for determining if unblinding of a subject's treatment assignment is warranted. Subject safety must always be the first consideration in making such a determination. If the Investigator decides that unblinding is warranted, every effort should be made to contact the Sponsor and Medical Monitor prior to unblinding a subject's treatment assignment unless this could delay emergency treatment of the subject. If a subject's treatment assignment is unblinded, the Sponsor must be notified within 24 hours after breaking the blind. The date and reason that the blind was broken must be recorded in the source documentation and electronic Case Report Form (eCRF), as applicable.

#### 5.4. Assessment Time Point Identifiers

In the data listings for the report, scheduled assessment time points will be identified as follows:

- Scheduled safety assessments will be identified by treatment group, study day, and also nominal study time point, where relevant.
- Assessments at Screening and End of Study will be identified as such for both study day and time-point, as appropriate.

#### 5.5. Data Derived by Calculation

The following data fields for inclusion in the data listings will be derived by calculation as per clinical data interchange standards consortium (CDISC) standard:

- Treatment-emergent Indicator for adverse event, assigned as  
Treatment-Emergent if  
 $(\text{Onset Date} + \text{Onset Time}) \geq (\text{Date of First Dose} + \text{Time of First Dose})$   
Non Treatment-Emergent if  
 $(\text{Onset Date} + \text{Onset Time}) < (\text{Date of First Dose} + \text{Time of First Dose})$
- Adverse event time since first dose (in days, to two decimal places), calculated as  
 $(\text{Onset Date} + \text{Onset Time}) - (\text{Date of First Dose} + \text{Time of First Dose})$

*AE Duration:*

- Adverse event duration (in days, to two decimal places), calculated as  
 $(\text{Resolution Date} + \text{Resolution Time} - \text{Onset Date} - \text{Onset Time})$

*Safety Assessments Change from Baseline:*

- Baseline for Vital Signs and serum clinical laboratory parameters will be the most recent scheduled assessment prior to first dose

*Clinical Safety Laboratory Assessments:*

- If a clinical laboratory result is above the upper limit of normal, then Out of Range flag will be set to "H"

- If a clinical laboratory result is below the lower limit of normal, then Out of Range flag will be set to “L”
- Clinical Laboratory parameters that are outside the reference range and assessed by the Principal Investigator as clinically significant will be identified as “Abnormal CS”
- Clinical Laboratory parameters that are outside the reference range and assessed by the Principal Investigator as not clinically significant will be identified as “Abnormal NCS”

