8.4 Adverse Events

All AEs will be recorded. At each post-Baseline Visit, subjects will also be questioned specifically about the status of any ongoing AEs.

The definitions of an AE or SAE can be found in [Appendix 4](#).

Adverse events will be reported by the subject (or, when appropriate, by a caregiver, surrogate, or the subject's legally authorized representative).

The Investigator and any designees are responsible for detecting, documenting, and recording events that meet the definition of an AE or SAE and remain responsible for following up AEs that are serious, considered related to the study medication or study procedures, or that caused the subject to discontinue the study (see [Section 7.0](#)). The trial blind may be broken for an individual only if knowledge of the IMP is essential for clinical management of the subject.

8.4.1 Time Period and Frequency for Collecting Adverse Event and Serious Adverse Event Information

All AEs and SAEs will be collected from signing the ICF until the Visit 6 (EOS) at the time points specified in the Schedule of Activities ([Section 1.2](#)).

All SAEs will be recorded and reported to the Sponsor or designee within 24 hours, as indicated in [Appendix 4](#). The Investigator will submit any updated SAE data to the Sponsor within 24 hours of it being available.

Investigators are not obligated to actively seek AE or SAE information after the conclusion of study participation. However, if the Investigator learns of any SAE, including a death, at any time after a subject has been discharged from the study, and he/she considers the event to be reasonably related to the study medication or study participation, the Investigator must promptly notify the Sponsor.

The methods of recording, evaluating, and assessing the causality of AEs and SAEs and the procedures for completing and transmitting SAE reports are provided in [Appendix 4](#).

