9.4.2 Safety Analyses

All subjects enrolled in the study who were dispensed study medication and who applied study medication at least once will be included in the analysis of safety and will be considered the Safety population.

All AEs reported during the study will be listed, documenting onset, whether therapy was required, any change in study treatment dosing, severity, possible relationship to study treatment, and outcome. Verbatim terms on the eCRFs will be linked to preferred terms (PTs) and system organ class (SOC) using the Medical Dictionary for Regulatory Activities (MedDRA) mapping system.

Treatment-emergent adverse events (TEAEs) are defined as AEs that first occur or worsen in severity after the first administration of study treatment and prior to 30 days after the last administration of study treatment. All reported TEAEs and incidence rates will be summarized by the number of subjects reporting AEs, SOC, PT, severity, and relationship to study treatment by treatment group.

Treatment-emergent AEs by maximum severity, TEAEs by relationship to study treatment, SAEs, TEAEs leading to death, and TEAEs leading to discontinuation of study treatment will be tabulated for each treatment group. Commonly occurring TEAEs, ie, those that occur in 5% or more of the subjects in either treatment group, will be summarized using descriptive statistics.

All laboratory test results, vital signs measurements, and weight will be summarized for each treatment group using descriptive statistics for raw numbers and change from Baseline. The incidence of treatment-emergent abnormal laboratory and vital signs values will also be summarized using descriptive statistics.

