- For each AE/SAE, the Investigator must document in the medical notes that he/she has reviewed the AE/SAE and has provided an assessment of causality.
- There may be situations in which an SAE has occurred, and the Investigator has minimal information to include in the initial report to IQVIA Biotech Safety. However, it is very important that the Investigator always make an assessment of causality for every event before the initial transmission of the SAE data to IQVIA Biotech Safety.
- The Investigator may change his/her opinion of causality in light of follow-up information and send an SAE follow-up report with the updated causality assessment.
- The causality assessment is one of the criteria used when determining regulatory reporting requirements.

Follow-Up of AEs and SAEs

- The Investigator is obligated to perform or arrange for the conduct of supplemental measurements and/or evaluations as medically indicated or as requested by IQVIA Biotech Safety to elucidate the nature and/or causality of the AE or SAE as fully as possible. This may include additional laboratory tests or investigations, histopathological examinations, or consultation with other health care professionals.
- If a subject dies during participation in the study or during a recognized follow-up period, the Investigator will provide IQVIA Biotech Safety with a copy of any postmortem findings including histopathology.
- New or updated information will be recorded in the originally completed eCRF.
- The Investigator will submit any updated SAE data to the Sponsor/IQVIA Biotech Safety within 24 hours of receipt of the information.

Reporting of SAEs

SAE Reporting to IQVIA Biotech Safety via Paper CRF

- E-mail transmission of the SAE paper CRF is the preferred method to transmit this information to IQVIA Biotech Safety with Facsimile transmission as back-up method.
- In rare circumstances and in the absence of e-mail/facsimile equipment, notification by telephone is acceptable with a copy of the SAE data collection tool sent by overnight mail or courier service.
- Initial notification via telephone does not replace the need for the Investigator to complete and sign the SAE eCRF pages within the designated reporting time frames.

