### 5.6.2. Adverse Events Missing Data Rules:

For adverse events with unknown intensity (severity) or unknown relationship to study treatment, these will be imputed as follows:

- If the intensity (severity) of an adverse event is unknown/missing, the intensity will be imputed for the summary of adverse events as being the highest intensity that is not immediately life-threatening or resulting in death, i.e. “Severe”.
- If the relationship to investigational product of an adverse event is unknown/missing, and the adverse event onset occurred after first dose, or if onset date/time is unknown and it cannot be determined if onset occurred prior to dosing the relationship will be imputed for the summary of adverse events as related.

For adverse events, where either the onset time or resolution time is unknown, time since first dose and duration will be imputed as follows:

- If onset date is unknown, and it cannot be confirmed that onset was prior to the start of dose administration, then the AE will be classified as treatment-emergent, with unknown time since first dose.

- If either the date of onset or the date of resolution is unknown, then duration will be shown as unknown.
- If onset time is unknown:
  - If the date of onset is known to be the date of first dose administration, and it is confirmed by a CRF comment or communication with the site that onset was prior to the start of dose administration, then the AE will be classified as not treatment-emergent.
  - If the date of onset is known to be same as the date of first dose administration, and it is confirmed by a CRF comment or communication with the site that onset was after the start of dose administration, then the AE will be classified as treatment-emergent and the time since first dose will be shown on the listing as “<1” day.
  - If the date of onset is known to be later than the date of first dose administration, then Time since first dose will be determined as the number of days since first dose, shown on the listing as “~n” days, where n is the number of days difference between the date of dose administration and the date of onset.
- If either the onset time or resolution time is unknown:
  - If the date of onset and the date of resolution are known to be the same, then Duration will be shown on the listing as “<1” day.

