## 8.2. Safety Data Presentation and Analysis

All clinical safety and tolerability data will be listed for each subject.

Safety data will be presented for all subjects in the safety analysis set and summarised by dose level / treatment group.

Safety data will be summarized descriptively in tabular form. Summaries of key safety data assessed over time may also be presented in graphical form, as appropriate. Where summaries include changes from baseline, the relevant baseline value will be determined as described in Section 5.5 above.

All treatment-emergent adverse events reported in this study will be presented using MedDRA terms, as coded per the Data Management Plan. AEs and SAEs with onset following administration of the investigational product will be summarised by dose level / treatment, grouped according to system organ class and preferred term, and tabulated with descriptive statistics, where appropriate, for number of subjects and number of AEs per category, for all AEs and for AEs deemed drug-related. AEs will also be summarised by severity and by relationship to investigational product. Where a subject has more than one AE for the same MedDRA category, the subject will be counted only once, for the AE of highest severity or least favourable relationship.

Prior and concomitant medication will be coded using the WHO Drug Dictionary (WHODrug), as coded per the Data Management Plan. The number and percentage of subjects taking prior medication, and concomitant medication will be summarised using frequency tables according to WHO Drug ATC Level 1 Code Description and the WHO Drug Dictionary Preferred Name. If a subject has more than one prior or concomitant medication coded to the same category, the subject will be counted only once.

Clinical laboratory parameters will be tabulated and summarised by dose level / treatment group and study time point. A summary of changes from baseline will also be presented for clinical laboratory parameters. Medical assessments of blood and urine parameters will be summarised by treatment group and study time point. Individual subject profiles will be presented for any laboratory parameters with at least one post-dose value outside the laboratory's reference ranges and deemed clinically significant.

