## 11. CHANGES FROM THE ANALYSIS PLANNED IN THE PROTOCOL

There are no changes from the planned analysis described in the protocol.

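### The SAP's treatment-emergent flag uses onset only; it omits the protocol's worsening criterion and 30-day limit, and the SAP declares no change

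*SAP*

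**What the plan says.** Protocol 9.4.2 gives this definition of a treatment-emergent event: "AEs that first occur or worsen in severity after the first administration of study treatment and prior to 30 days after the last administration". An AE can therefore qualify by first occurring or by worsening, and there is an upper time limit.

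SAP 5.5 sets out the flag under the words "Treatment-emergent Indicator for adverse event, assigned as" and derives it from one comparison. An AE is treatment-emergent if its onset date and time are at or after those of the first dose. Every AE with an earlier onset falls under "Non Treatment-Emergent if". Severity plays no part and there is no end date.

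SAP 8.2 repeats the onset basis for the tables: "AEs and SAEs with onset following administration of the investigational product will be summarised by dose level / treatment". The AE missing-data rules in SAP 5.6.2 deal with an unknown onset ("If onset date is unknown, and it cannot be confirmed that onset was prior to the start of dose administration") and do not mention worsening.

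SAP 11 states: "There are no changes from the planned analysis described in the protocol".

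**The concern.** The two documents give different definitions of the population of events in the main safety tables, and the SAP says they do not differ. A programmer following SAP 5.5 will produce a flag that is too narrow at one end, because worsening of a pre-dose AE is ignored. It is too wide at the other, because late events are kept.

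Safety is one of the study's two objectives, and the sample size section says the study should help choose the Phase 3 dose. The tables by severity and by relationship will be read as following the protocol definition. An undeclared departure means that a reader of the study report cannot tell which definition was used.

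**Working it through.** The plan gives no figure to reproduce, so the check compares the two rules directly.

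**Rules.** Let *t* be days since first dose (first dose at *t* = 0) and *L* the day of the last dose.
- SAP 5.5: treatment-emergent if onset ≥ 0.
- Protocol 9.4.2: treatment-emergent if onset, or an increase in severity, lies after 0 and before *L* + 30.

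**Five hypothetical AE records.** *L* = 84 for A to D and *L* = 20 for E.

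| Record | SAP 5.5 | Protocol 9.4.2 |
|---|---|---|
| A. Onset *t* = −10, no worsening | No | No |
| B. Onset *t* = −10, worsens at *t* = 20, one record with original onset | No | Yes |
| C. Same course, but worsening entered as a new AE with onset *t* = 20 | Yes | Yes |
| D. Onset *t* = 20 | Yes | Yes |
| E. Last dose *t* = 20, new onset *t* = 60 | Yes | No (window closes at 20 + 30 = 50) |

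The rules disagree on B and E. Records B and C describe the same clinical course and differ only in how it was entered.

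**Can record B arise?** Protocol 8.4.1 collects AEs from signature of consent, and screening may last up to 90 days, so pre-dose AEs can exist. Footnote k of the Schedule of Activities sends health changes in screening and washout to medical history, unless the event was unanticipated and resulted from a study procedure. Those exceptions are the pre-dose AEs that remain. Neither document says whether a later rise in severity opens a new record. Protocol Appendix 4 says, under follow-up, "New or updated information will be recorded in the originally completed eCRF", and elsewhere asks for each event to be recorded separately. Neither sentence mentions severity increases or onset dates.

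**Can record E arise?** Routine AE collection ends at Visit 6, on Day 85 ± 7. Day 1 is the first dose, so that is *t* = 84, or *t* = 91 at the end of the window. The 30-day limit can bind only if *L* + 30 falls on or before that visit. That requires *L* ≤ 84 − 30 = 54, or *L* ≤ 91 − 30 = 61 at the latest. The subject must therefore stop treatment at least 30 days before the final visit and stay under observation.

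**Which outputs are affected?** Tables 14.3.1.1 to 14.3.1.5 are titled as treatment-emergent. Table 14.3.1.6 and the tables under 14.3.2 are not, so they are not counted here. Listing 16.2.7.1 shows AEs whatever the flag says.

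**The case against.** The strongest reply is that the mismatch has little practical effect, and much of that stands.

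- **Medical history absorbs most pre-dose events.** Section 8.4.1 ties collection to the Schedule of Activities, so footnote k applies to it. A reader might infer that nothing limits the number of pre-dose AEs; the footnote does limit it.
- **Worsening of a medical-history condition is already captured.** Appendix 4 treats exacerbation of a pre-existing condition as an AE, and Protocol 8.3.1 records worsened examination findings at Visit 6 as AEs. These have a post-dose onset, and SAP 5.5 flags them.
- **Skin irritation is measured elsewhere.** A reader might infer that aggravation of diseased skin by a topical retinoid would be hidden. The listed local skin reactions are graded before the first application and at each later visit, and SAP 8.2 tabulates them as worsened or not. They become AEs only if they need medical intervention or withholding of study medication (Protocol 8.3.3 and 8.4.7).
- **Appendix 4 does not settle the recording question.** A reader might infer that the onset must stay pre-dose because updates go into the original form. That sentence is a general follow-up instruction. The eCRF completion rules are not in the documents, so record B is possible but not established.
- **One subject in 15 is not an effect size.** A reader might cite 1/15 = 6.7 percentage points as the bias in an arm. That is only the weight of one subject. The arm's overall rate moves only if the subject has no other treatment-emergent AE, and the number of such subjects is unknown.

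These points limit how often the flag would be wrong. They do not make the definitions agree or make the SAP 11 statement correct. Record C shows that entering each increase as a new AE would rescue the SAP rule for worsening, but neither document requires that, and it would not restore the upper limit.

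**Conclusion.** The definitional discrepancy is certain from the text: SAP 5.5 and 8.2 omit two elements of the definition in Protocol 9.4.2, and SAP 11 does not declare it. The errors run in opposite directions. A pre-dose AE that worsens under its original record is missed in five tables, and a late-onset AE in a subject who stopped early is wrongly included.

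The affected group is probably small, and its size cannot be computed from the documents. The first error requires both a recorded pre-dose AE and severity increases kept in the original record. The second requires continued follow-up for at least 30 days after the last dose. Nothing is lost from the AE listings. This is a correction to make for accuracy and consistency, not evidence that the safety conclusions would be materially biased.

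**What to change.** Align SAP 5.5 and 8.2 with Protocol 9.4.2. An AE is treatment-emergent if its onset, or an increase in severity of a pre-dose AE, falls at or after the first dose and before 30 days after the last dose.

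State how a severity increase is recorded and capture its date, so that the flag can be derived. A dated severity change on the original record, or a new linked record, would serve, provided the derivation matches the convention chosen.

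If the sponsor prefers the onset-only rule, SAP 11 should declare the departure and give the reason.

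The cost is a few words in two SAP sections, one derivation, and a note in the eCRF completion instructions. It should be done before database lock; no clinical rule changes.
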